10.0 STATISTICAL CONSIDERATIONS

10.1 Phase I

The primary objective of the phase I portion of this study is the determination of the MTD of IMRT when used in conjunction with IV busulfan and VP-16 as a conditioning regimen for allogeneic stem cell transplantation for patients meeting the specified eligibility requirements. The definition of dose limiting toxicity and MTD are given in section 7.1. The number of patients to be treated at each dose level in the phase I trial and the rules for dose escalation are given 7.2. This study is likely to require 18 patients per stratum if the highest dose is well tolerated. It should take approximately 12-18 months to complete this portion of the trial.

The toxicities observed at each dose level will be summarized in terms of type (organ affected or laboratory determination such as absolute neutrophil count), severity (by NCI CTCAE v3.0 and nadir or maximum values for the laboratory measures), date of onset, duration, reversibility, and attribution. Tables will be created to summarize these toxicities and side effects by dose level. Baseline information (e.g., the extent of prior therapy) and demographic information will be presented, as well, to describe the patients treated in this study. All disease responses will be reported. Survival and time to failure will be summarized both by pooling across dose levels and within each dose level, although the primary outcome of the phase II portion will include only patients accrued at the MTD.

10.2 Phase II

An aim of this study is to estimate the efficacy of this regimen in eligible patients. The study is designed to estimate whether 1) the relapse rate and disease-free survival probability at two years is broadly comparable to that obtained with conventional treatment, and 2) to establish whether the more selective radiation targeting yields an improvement in the incidence duration and severity of mucositis. The primary endpoints

will be relapse rate to be estimated for informal comparison to published historical rates, and the fraction of patients experiencing grade 3-5 mucositis. While mucositis grading is subject to variability, 100% of comparable patients receiving previous preparatory regimens involving TBI experience unequivocal high-grade mucositis.

For the adult stratum: the phase II portion will enroll 30 additional patients to the MTD established in the phase I trial, in order to estimate the two-year relapse rate to an accuracy of 18% with 95% confidence (s.e. = 9.1%). If, as hoped, the true (long-run) mucositis rate is better than 70%, there would likely be (e.g., with >95% probability) at least 5 subjects spared high-grade mucositis, which would be a highly significant improvement (p < 0.002) compared to historical data (0 out of > 70). Based on the current referral patterns to the City of Hope, it is expected that approximately 6-10 patients per year will be eligible for this study. With a goal of 30 additional patients treated at the MTD, (23 patients already treated) approximately one and a half year of accrual will be required just for the phase II portion.

For the pediatric stratum: the phase II portion will be an exploratory analysis conducted to characterize outcomes for the pediatric population. In addition to the six pediatric cases treated at the 'pediatric' MTD (which may different from the adult population), additional pediatric patients will be enrolled and treated at the MTD, with a maximum of nine additional pediatric patients enrolled during the phase II portion of the study.

10.3 Phase II Monitoring

Early stopping rules are incorporated into the phase II portion of the study for excessive toxicity. However there will be no interim analysis for efficacy during the phase II stage. Toxicities will be recorded using two distinct grading systems; the modified Bearman Scale (Bearman, S., et al, JCO, Vol 6, No 10 (Oct), 1988, pp1562-1568. See appendix X for details.) and the NCI CTCAE 3.0 Scale.

Generally, the modified Bearman Scale will be used to define (grade) 'early stopping' events (toxicities), and the NCI CTCAE 3.0 Scale will be used for reporting adverse events. The only exception relates to how hematologic toxicities are graded and incorporated into the early stopping criteria. For hematologic toxicities the CTCAE 3.0 Scale will be used. The table below will be consulted as relevant toxicities are encountered, so there will be no accrual-based interim analysis point.

Early Stopping Criteria: For each adverse outcome, stop if the cumulative number of patients reaches or exceeds the following limits:

Table of Early Stopping C	Criteria				
# of patients treated at the MTD	# of patients expired due to treatment	# of patients with grade 3 toxicities that would require an	Probability stopping r given a fa	ule will be	invoked
	related causes that would stop the study*	evaluation for safety per Bearman Scale**	10%	15%	20%
12	3	3	0.11	0.26	0.45
18	5	5	0.12	0.27	0.47
24	6	6	0.12	0.31	0.53
30	8	8	0.13	0.31	0.53

36	9	9	0.13	0.32	0.55
* Note: The stopping rules are	not statistically based; expec	ted treatment related mortalit	y should not	to exceed 2	5%.

** Note: For hematologic toxicities: Any grade 4 neutropenia associated with fever or infection and lasting beyond three weeks, or grade 4 neutropenia lasting for more than 28 days per CTCAE 3.0 toxicity criteria should be counted toward the early stopping rule.

Any patient who receives treatment as part of the phase II portion of this protocol will be evaluable for toxicity. Each patient will be assessed periodically according to the treatment schedule for the development of any toxicity. The toxicity rule for safety will be assessed as each patient reaches day +30 post transplantation. If more than the specified number of patients (noted in the table above) have significant treatment related toxicities, then the safety of the study will be evaluated.

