16.0 DATA AND SAFETY MONITORING PLAN

A. Definition of Risk Level

This is a risk level 4 study as defined in the Guidance Policy and Procedures for Data and Safety Monitoring for In-House trials at City of Hope. http://www.infosci.coh.org/gcrc/doc/dsmp.doc This study involves tissue transplant and chemotherapy.

B. Monitoring and Personnel Responsible for Monitoring

The Protocol Management Team (PMT) consisting of the PI, Collaborating Investigator(s), CRA/protocol nurse and statistician are responsible for monitoring the data and safety of this study, including implementation of the stopping rules for safety and efficacy, including implementation of the stopping rules for safety and efficacy (see section 10.3).

For phase I of the trial, monitoring by the PMT will be done using the phase I tracking log, the objective will be to monitor data and safety for dose escalation. Data and safety will be reported to the City of Hope DSMB after each dose level, and the PMT will decide before patients are enrolled on the phase II portion of the trial.

For phase II of the trial, data and safety will be reported to the City of Hope DSMB annually. In addition to the annual report, any early evaluations for safety and/or treatment related mortality will also be reported as these assessments are made (per guidelines set in section 10.3 and 10.4 of the protocol). This report (the PMT report) will include a summary of accrual, adverse events and treatment related mortality.

C. Adverse Events

The frequency for the recording of toxicities are outlined in Appendix V and Appendix X.

C.1. Reporting

Adverse events must be reported to the City of Hope DSMB and IRB according to definitions and guidelines at http://www.infosci.coh.org/gcrc/doc/dsmp.doc and http://resadmin.coh.org/doc/irb3810.doc which are defined below. SAE's will be monitored by the PMT. Less than serious adverse events will be reported only at the time of protocol continuation reports. All AE's occurring during the study will be recorded in the CRF. Grade 3, 4 toxicity will be reported to the IRB except Grade 3, 4 laboratory abnormalities which will be reported only if clinically significant.

C.2. Adverse Event

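### Section 10.3 gives two different triggers for the same grade 3 toxicity limits, one patient apart in every row, and the 12-patient probabilities fit only the earlier trigger

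*Combined protocol and SAP*

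**What the plan says.** All of the conflicting text is in section 10.3 (Phase II Monitoring).

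- **Lead-in to the table:** "For each adverse outcome, stop if the cumulative number of patients reaches or exceeds the following limits". This covers deaths and toxicities alike.
- **Toxicity column heading**, broken over lines in the available text: the number "of patients with grade 3 toxicities that would require an" and then "evaluation for safety per Bearman Scale". The limits are 3, 5, 6, 8 and 9 at 12, 18, 24, 30 and 36 patients, the same as in the treatment-related death column. One set of probabilities, for true rates of 10%, 15% and 20%, is printed beside both columns.
- **Closing sentence:** "If more than the specified number of patients (noted in the table above) have significant treatment related toxicities". The consequence it attaches to that condition is a safety evaluation and not a stop.
- **Timing:** "The table below will be consulted as relevant toxicities are encountered, so there will be no accrual-based interim analysis point", and later "The toxicity rule for safety will be assessed as each patient reaches day +30 post transplantation".

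Section 16.0, part B, provides for monitoring by the protocol team and annual phase II reports to the DSMB. It adds that "any early evaluations for safety and/or treatment related mortality will also be reported as these assessments are made", pointing back to section 10.3.

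**The concern.** The lead-in acts when the count equals the limit. The closing sentence, which points to the same table, acts only when the count is above it. For toxicity that is 3 against 4 of 12, 5 against 6 of 18, 6 against 7 of 24, 8 against 9 of 30, and 9 against 10 of 36. Nothing in the plan says which governs.

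The consequence is also inconsistent. The lead-in stops the study for any adverse outcome, whereas the toxicity heading and the closing sentence call for a safety evaluation.

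This table is the only numerical safety rule in phase II. Because section 16.0 has early safety evaluations reported as they are made, the wording decides whether the third toxicity in 12 patients, or only the fourth, leads to an evaluation and a report outside the annual cycle. If the closing sentence is followed, the rule in use is weaker than the printed probabilities suggest.

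**Working it through.** **Inputs, all from the section 10.3 table.** Limits c = 3, 5, 6, 8, 9 at n = 12, 18, 24, 30, 36; true rates p = 0.10, 0.15, 0.20; and the 15 printed probabilities. The lead-in is read as X ≥ c, and the closing sentence as X > c, that is X ≥ c + 1.

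**Step 1: the 12-patient row.** No earlier row enters here, so each reading is a single binomial tail with X ~ Bin(12, p):

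P(X ≥ 3) = 1 − [P(0) + P(1) + P(2)], and P(X ≥ 4) = P(X ≥ 3) − P(3).

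- p = 0.10: 1 − (0.2824 + 0.3766 + 0.2301) = 0.111. Subtracting P(3) = 0.0852 gives 0.026.
- p = 0.15: 1 − (0.1422 + 0.3012 + 0.2924) = 0.264. Subtracting P(3) = 0.1720 gives 0.092.
- p = 0.20: 1 − (0.0687 + 0.2062 + 0.2835) = 0.442. Subtracting P(3) = 0.2362 gives 0.205.

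The printed values are 0.11, 0.26 and 0.45. The ≥ reading reproduces them within 0.01. The > reading gives about 23%, 35% and 46% of the printed values.

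**Step 2: later rows, limits tested at the five tabulated sample sizes.** The probability of having triggered by each row comes from an exact binomial recursion that removes paths that have already triggered. Each cell shows p = 0.10 / 0.15 / 0.20.

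| n | Printed | ≥ limit | > limit |
|---|---|---|---|
| 12 | 0.11 / 0.26 / 0.45 | 0.111 / 0.264 / 0.442 | 0.026 / 0.092 / 0.205 |
| 18 | 0.12 / 0.27 / 0.47 | 0.115 / 0.280 / 0.473 | 0.027 / 0.102 / 0.234 |
| 24 | 0.12 / 0.31 / 0.53 | 0.121 / 0.304 / 0.523 | 0.030 / 0.120 / 0.285 |
| 30 | 0.13 / 0.31 / 0.53 | 0.121 / 0.308 / 0.535 | 0.030 / 0.123 / 0.298 |
| 36 | 0.13 / 0.32 / 0.55 | 0.122 / 0.316 / 0.557 | 0.031 / 0.130 / 0.325 |

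Under ≥, all 15 cells are within 0.01 of print (largest gap 0.010). Under >, none is (smallest gap 0.084, largest 0.245). Checking after every patient against the limit of the row still to come gives identical values, because a count that reaches the limit early is still at or above it when that row is reached.

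**Step 3: the other plausible schedule.** Section 10.3 also has the rule assessed as each patient reaches day +30. If it is checked after every patient and each row's limit stays in force until the next row, the results are:

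| n | ≥ limit | > limit |
|---|---|---|
| 12 | 0.111 / 0.264 / 0.442 | 0.026 / 0.092 / 0.205 |
| 18 | 0.238 / 0.480 / 0.690 | 0.083 / 0.244 / 0.451 |
| 24 | 0.243 / 0.494 / 0.711 | 0.085 / 0.257 / 0.478 |
| 30 | 0.249 / 0.514 / 0.742 | 0.089 / 0.278 / 0.522 |
| 36 | 0.250 / 0.518 / 0.748 | 0.090 / 0.281 / 0.532 |

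Only 3 of 15 cells (the 12-patient row) fit within 0.01 under ≥, and 1 of 15 under >. Neither trigger reproduces the table on this schedule. The 12-patient row is the same under both schedules, so the result in step 1 does not depend on the choice.

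**The case against.** The strongest counter-argument is that the probabilities may not describe toxicity at all. Their header is cut off in the available text. What survives refers to a stopping rule being invoked, and only the death column is headed as stopping the study. If they describe deaths alone, the closing sentence contradicts no printed number. This cannot be excluded. Against it, both columns share the same limits, there is one set of probabilities, and the footnote on neutropenia counts those events toward the early stopping rule. The wording conflict remains either way, and on the deaths-only reading the toxicity rule would have no printed operating characteristics.

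A second objection is that the sentences concern different actions, stopping and evaluating. That explains the loose verb in the lead-in but not the difference in threshold. The toxicity heading gives its numbers as counts that require an evaluation, so by the heading 3 of 12 requires one and by the closing sentence it does not.

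Third, the fit is approximate: rounded to two decimals, only 8 of 15 printed values agree exactly with the ≥ recursion. That is correct, but the > reading misses every cell by at least 0.084 on the same schedule.

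Fourth, no printed figure is shown to be wrong, a footnote says the stopping rules have no statistical basis, and other safety monitoring exists. These points limit the weight of the finding. The death rule is unaffected, and for toxicity the closing sentence leads to an evaluation and not to automatic closure. They do not tell staff which count to act on.

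**Conclusion.** The concern holds. Section 10.3 gives two triggers for one set of toxicity limits, one patient apart in every row, with two stated consequences. Confidence is high on this conflict and on the 12-patient figures.

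Confidence is moderate on the later rows, which depend on the unstated look schedule. With limits tested at the five tabulated sample sizes and a true rate of 20%, the chance of triggering by 36 patients is 0.557 under the lead-in and 0.325 under the closing sentence, against 0.55 printed. With limits carried forward, the figures are 0.748 and 0.532.

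The comparison with the printed probabilities assumes that they apply to the toxicity column. This should be fixed; it is a defect in wording and consistency, and the treatment-related death limits are not touched by it.

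**What to change.** The sponsor should reconcile the lead-in, the toxicity heading and the closing sentence of section 10.3 to one toxicity trigger and one stated consequence. The section should also say which limit applies between the tabulated sample sizes. Which trigger to adopt is the sponsor's decision.

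- If the printed probabilities are meant to describe the toxicity rule, the closing sentence has to act at the specified number or above.
- If action only above the number is kept for toxicity, that column needs its own probabilities: 0.03, 0.09 and 0.21 at 12 patients, with later rows computed under the stated schedule.

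The cost is a short wording amendment. New toxicity probabilities are needed only if the above-the-limit trigger is kept or limits are carried forward between rows.

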10.4 Analysis of Clinical Endpoints

There will be one combined statistical analysis for efficacy. In accordance with the primary study objectives, we will perform descriptive statistical analyses on these data after the phase II study is complete. Our primary endpoints will be OS, RFS, EFS, TRM, and RR with infection and acute- chronic- GVHD as secondary endpoints. Confidence Intervals will be estimated by calculating exact 95% confidence limits for a binomial parameter. The time-to-event endpoints, such as RFS and OS, will be estimated using the product limit method of Kaplan-Meier and tested using the Log-Rank test.

11.0 REGISTRATION GUIDELINES

Once a signed informed consent has been obtained and all pre-treatment evaluations have been performed, patients will be entered on study after review of patient eligibility criteria by the assigned Clinical Research Associate from the City of Hope Department of Biostatistics. Patients may be screened for registration by calling the Department of Biostatistics at [name].

12.0 RECORDS TO BE KEPT AND DATA SUBMISSION SCHEDULE

- 12.1 Confidentiality of Records: The original data collection forms will be stored in secured cabinets in the Department of Biostatistics.
- 12.2 Patient Consent Form: At the time of registration, three signed and dated copies of the patient Informed Consent form with the Human Rights must be available (for patient, patient's medical chart, and one for the City of Hope Biostatistics Office).

13.0 WOMEN AND MINORITIES GUIDELINES

All eligible patients from both genders and from all racial/ethnic groups will be recruited equally into this trial, with the only exclusionary criteria being those stated in Section 5.0. Based on our patient populations and previous experience with BMT for advanced hematological malignancies, the anticipated rates of entry into this study by gender and race/ethnicity are as follows:

	American Indian or Alaskan Native	Asian or Pacific Islander	Black, not of Hispanic Origin	Hispanic	White, not of Hispanic Origin	Other or unknown
Female	0%	8%	1%	32%	58%	1%
Male	<1%	8%	3%	33%	54%	3%
Total	<1%	8%	2%	33%	55%	2%

Race/Ethnicity by Gender for Advanced Malignancy Patients Receiving HSCT at City of Hope

14.0 DATA MANAGEMENT

The assigned Clinical Research Associate from the Department of Biostatistics will maintain all primary data, including eligibility checklist, pre-study and initial data forms, consolidation, transplant data, pathology reports and off-study information. Data will be collected by the CRA at the time of each patient evaluation. Records will be stored in a secure location within the Biostatistics Department. See Study Calendar and Appendix XI for time points for grading toxicities.

15.0 ETHICAL AND REGULATORY CONSIDERATIONS

This study is to be approved by the Institutional Review Board (IRB) according to City of Hope ethical and regulatory guidelines. All patients will have signed an informed consent for participation in research activities, and will have been given a copy of the Experimental Subject's Bill of Rights.

When results of this study are reported in medical journals or at meetings, identification of those taking part in this study will be withheld. The medical records of subjects will be maintained in strictest confidence, according to current legal requirements. However, these records will be made available for review, as required by the Food and Drug Administration (FDA) or other authorized users such as the National Cancer Institute (NCI), under the guidelines established by the Federal Privacy Act.

16.0 DATA AND SAFETY MONITORING PLAN

A. Definition of Risk Level

This is a risk level 4 study as defined in the Guidance Policy and Procedures for Data and Safety Monitoring for In-House trials at City of Hope. http://www.infosci.coh.org/gcrc/doc/dsmp.doc This study involves tissue transplant and chemotherapy.

B. Monitoring and Personnel Responsible for Monitoring

The Protocol Management Team (PMT) consisting of the PI, Collaborating Investigator(s), CRA/protocol nurse and statistician are responsible for monitoring the data and safety of this study, including implementation of the stopping rules for safety and efficacy, including implementation of the stopping rules for safety and efficacy (see section 10.3).

For phase I of the trial, monitoring by the PMT will be done using the phase I tracking log, the objective will be to monitor data and safety for dose escalation. Data and safety will be reported to the City of Hope DSMB after each dose level, and the PMT will decide before patients are enrolled on the phase II portion of the trial.

For phase II of the trial, data and safety will be reported to the City of Hope DSMB annually. In addition to the annual report, any early evaluations for safety and/or treatment related mortality will also be reported as these assessments are made (per guidelines set in section 10.3 and 10.4 of the protocol). This report (the PMT report) will include a summary of accrual, adverse events and treatment related mortality.

C. Adverse Events

The frequency for the recording of toxicities are outlined in Appendix V and Appendix X.

C.1. Reporting

Adverse events must be reported to the City of Hope DSMB and IRB according to definitions and guidelines at http://www.infosci.coh.org/gcrc/doc/dsmp.doc and http://resadmin.coh.org/doc/irb3810.doc which are defined below. SAE's will be monitored by the PMT. Less than serious adverse events will be reported only at the time of protocol continuation reports. All AE's occurring during the study will be recorded in the CRF. Grade 3, 4 toxicity will be reported to the IRB except Grade 3, 4 laboratory abnormalities which will be reported only if clinically significant.

C.2. Adverse Event

An adverse event (AE) is any untoward medical experience or change of an existing condition that occurs during or after treatment, whether or not it is considered to be related to the protocol intervention. All AEs occurring during this study, whether observed by the physician, nurse, or reported by the patient, will be recorded on the City of Hope National Medical Center Adverse Events (CTCAE version 3.0) form.

C.3. Serious Adverse Event

A serious adverse event (SAE) is defined as *any expected or unexpected adverse event* (AE, generally equivalent to CTCAE grades 3, 4 or 5) that is *related or unrelated* to the intervention that results in any of the following outcomes:

- Death
- A life-threatening event
- In-patient hospitalization (not required as part of the treatment) or prolongation of existing hospitalization
- A persistent or significant disability/incapacity
- A congenital anomaly/birth defect
- Causes cancer
- Is an overdose

Certain medical events that may not result in death, be life-threatening, or require hospitalization, may also be considered a serious adverse event when appropriate medical or surgical intervention is necessary to prevent one of the outcomes listed above.

C.4. Unexpected Adverse Event

Any event in which the severity or specificity is not consistent with the risk information described in the protocol, and the event is not anticipated from the subject's disease history or status.

C.5. Expected Adverse Event

Any event in which the severity or specificity is consistent with the risk information described in the protocol or is anticipated based on the subject's medical history.

C.6. Attribution

For reporting purposes, attribution is the assessment of the likelihood that an AE is caused by the research agent or protocol intervention. The attribution is assigned by the Principal Investigator after considering the clinical information, the medical history of the subject, and past experience with the research agent/intervention. This is recorded using the Adverse Event Report (COH AER) form (http://resadmin.coh.org/doc/irb3820.doc) in one of 5 categories scored as the following: 5=related, 4=probably related, 3=possibly related, 2=unlikely related and 1=unrelated. The attribution is subject to change as follow-up information becomes available, and it can be changed by the DSMB or by the IRB in the process of review.

17.0 REFERENCES:

